15.2 Determination of Sample Size

A formal sample size calculation was not performed for the primary objective of the study. Instead, the sample size 48 patients overall (N=12 for each dose level) was chosen to provide sufficient data for this pilot study of MOTREM in patients with septic shock. This is in line with recommendations for sample size of pilot studies (23).

As this is an exploratory study no adjustments for multiplicity will be employed.

15.3 Randomisation Methods

The randomisation lists will be performed by Ascopharm Statistician using SAS software Version 9.4 (Copyright© 2013 by SAS Institute Inc., Cary, NC, USA) with the procedure “PROC PLAN” before the start of the study.

Randomisation lists produced will be implemented into the randomisation module of the Ennov Clinical© software (V7.5 or higher).

The first randomisation list for the stage 1 will be created with a minimum of 3 randomisation blocs of 4 i.e. 12 patients. Each sequential cohort (0.3, 1.0 and 3.0 mg/kg/h of MOTREM) will contain 4 patients (3 active and 1 placebo). Patient satisfying eligibility criteria will be randomised in a 3:1 ratio per cohort to the treatments as specified below:

- MOTREM
- Placebo

The second randomisation list for the stage 2 will be created with a minimum of 9 randomisation blocs of 4 i.e. 36 patients. Each dose group will contain 9 patients. Patient satisfying eligibility criteria will be randomised in a 1:1 ratio to the treatments as specified below:

- Dose level 1
- Dose level 2
- Dose level 3
- Placebo

For security, the two randomisation lists will be extended over the number of patients initially planned. For example, for the stage 1, three extra cohorts of 4 patients each will be planned as cohorts could be repeated once.

A randomisation list will be provided to the site’s pharmacy, who is in charge of blinding and labelling of the treatments.

15.4 Interim Analysis

One unblinded interim analysis of complete 28-Day data is planned, after the end of study visit (D28) is complete for all patients, while the study is still ongoing. Some exploratory biomarker and ADA data may not be included in the interim analysis.

The study will be unblinded after the last subject completes the EOS visit and the interim database is available, including cleaned and locked data up to EOS visit (except possibly some of the biomarkers/ADA results). All parties (sponsor, investigators and subjects) may be unblinded at the time of this interim analysis.

The purpose of this interim analysis is to gather preliminary information in order to trigger possible external business decisions. The study will not be stopped early on the basis of this interim review.

Details for this interim analysis will be specified in the statistical analysis plan (SAP). The SAP will be finalised prior to unblinding.

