8.4.1 Data Safety Monitoring Board (DSMB)

An independent data safety monitoring board (DSMB) will monitor the safety of the study. The DSMB will comprise experts with experience in the treatment of sepsis and septic shock and the conduct of clinical trials in this indication. The DSMB will be responsible for:

- Examining blinded accumulated safety and PK data, with no formal statistical analysis performed, in order to make recommendations for the progression of the study to next dose (stage 1) or progression from stage 1 to stage 2.
- Reviewing serious adverse events (SAEs) and toxicity data
- Reviewing the general progress of the clinical study with regard to accrual/withdrawals or drop-out rates and clinical study conduct.

Where necessary, DSMB members may have access to unblinded safety data for one or more patients; however, no members of the study team (at INOTREM, at the Contract Research Organisation [CRO] or the sites) will have access to unblinded data until after database lock is declared. In case unblinded data needs to be handled or analysed before database lock, these tasks will be performed by persons independent from the study team.

The DSMB will provide recommendations for stopping or continuing the study based on safety results. The roles, responsibilities, and operating procedures of the DSMB will be formally defined in a DSMB charter which will be developed in consultation with DSMB members.

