11.3.5 Follow-up Period

A follow-up visit will be performed at 90 ± 2 days after the initiation of MOTREM treatment. A documented phone call to patient or carer is acceptable for this purpose.

The following assessments will be performed:

- Mortality
- Relevant changes to patient's condition

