17.2 Clinical Database

Data Management will create the database under Oracle (V10.2.04 or higher) and the eCRF entry screens.

The eCRF application will be accessible by connecting on a dedicated and secure website using Clinsight Online module. Each user will connect by using personal identifier / password.

The Data Manager will write the Data Handling Manual (DHM) which describes the various data management steps, the database structure (name and format of the items) and the annotated eCRF, and the validation plan.

The investigator, sub-investigators or its designated representative will enter the data for each patient on online eCRF application. The data will be extracted from the ORACLE database and formatted as SAS files (V9.4).

The Data Manager will program the consistency checks defined in the validation plan. These checks will result in the production of Electronic Data Clarification Forms (eDCFs). The investigator or designated representative will directly answer to these eDCFs on the eCRF application.

Adverse events will be coded using MedDRA dictionary, and concomitant treatment will be coded using WHO-DRUG dictionary version 2015-3 or higher.

At the end of the validation process, the Data Manager will produce listings which describe all protocol deviations. The status of these deviations (minor or major) will be discussed during the pre-analysis review, and the analysis population will be defined.

At the end of the data management process, the database will be frozen and the SAS files will be sent to INOTREM SA according to the Data transfer process.

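### Section 15.4 allows sponsor, investigators and patients to be unblinded after the last Day 28 visit, with Day 90 and possibly some assays outstanding, and the protocol does not say which database lock releases the blind

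*Combined protocol and SAP*

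**What the plan says.** Section 15.4 schedules a single unblinded analysis "after the end of study visit (D28) is complete for all patients, while the study is still ongoing". On timing it states that "The study will be unblinded after the last subject completes the EOS visit and the interim database is available". The interim database is to be cleaned and locked up to the Day 28 visit, with a possible exception for some assay results: "Some exploratory biomarker and ADA data may not be included in the interim analysis". On access it states that "All parties (sponsor, investigators and subjects) may be unblinded at the time of this interim analysis". The stated purpose is to inform external business decisions. The study will not be stopped early on this review, and the SAP must be final before the codes are opened.

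Three other sections bear on this:

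- **8.4.1:** no study-team member at the sponsor, the CRO or the sites "will have access to unblinded data until after database lock is declared". Unblinded work needed before then goes to people independent of the team.
- **10.6.1:** the randomisation list is filed when the study is complete, after a lock and after the blind is revealed. It mentions one lock and no interim one.
- **17.2:** protocol deviations are listed at the end of data validation, and then "The status of these deviations (minor or major) will be discussed during the pre-analysis review, and the analysis population will be defined". The database is frozen after that.

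The Day 90 visit (11.3.5) records mortality and relevant changes in the patient's condition. "A documented phone call to patient or carer is acceptable for this purpose".

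**The concern.** A double-blind study protects data only while the people who collect and classify them do not know the allocation. Section 15.4 lets that protection end for the sponsor, the investigators and the patients while some data are still to come. Sections 8.4.1 and 10.6.1 read as though it lasts until the database is locked.

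Three things could be affected:

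- how completely late follow-up is obtained;
- what a patient, carer or investigator reports as a change in condition at Day 90, possibly by telephone;
- which patients are excluded from the PD set, where that depends on assays still outstanding.

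The business purpose given in 15.4 does not require investigators or patients to know the allocation, so the breadth of the permission gains nothing that the plan states.

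**Working it through.** **1. Which lock releases the blind?** The protocol does not define the term, so both readings were followed through.

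- *Final lock.* Section 10.6.1 ties its one lock to study completion. Section 8.3 defines the end of study as the last patient's last visit. Section 11.3.4 calls Day 28 the End of Study visit, but 15.4 itself says that the study is still ongoing then and calls its source an interim database. On this reading 15.4 lets sponsor and investigators see allocation before 8.4.1 allows it, and does not use the independent-persons route.
- *Interim lock.* If the Day 28 lock satisfies 8.4.1, the sections agree for data up to Day 28. Day 90 data and the excepted assay results still fall outside that lock.

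Both readings leave something to repair.

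**2. How many patients have Day 90 pending?**

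Inputs:

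- N = 48 (9.1, 15.2). This reproduces: 3 cohorts x 4 + 4 arms x 9 = 12 + 36 = 48, with 3 + 9 = 12 per group, placebo included (3 x 1 + 9).
- Recruitment of 9-12 months (8.3).
- Visits at 28 ± 2 and 90 ± 2 days (11.3.4, 11.3.5).
- Assumptions: even accrual, and 30.44 days per month.

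Formula: pending = (N / recruitment months) x (90 - 28 - c) / 30.44, where c is the number of days from the last Day 28 visit until the interim database is available.

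- Accrual rate: 48/12 = 4.0 and 48/9 = 5.33 patients per month.
- c = 0: 62/30.44 = 2.04 months, giving 8.1 to 10.9 patients (17% to 23%). With the visit windows the gap is 58 to 66 days, giving 7.6 to 11.6.
- c = 28 (assumed): 34/30.44 = 1.12 months, giving 4.5 to 6.0 patients.
- c = 62 or more: about zero.
- At the maximum of 66 patients with c = 0: 11.2 to 14.9, the same percentages.

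Because 15.4 waits for the interim database, c exceeds zero, and 8-11 is the upper figure under even accrual.

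**3. What is exposed?**

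- *Day 90.* Of the two items collected, only mortality is an endpoint in 15.1.3. It is objective once ascertained, though completeness of ascertainment is less protected.
- *Late assays.* ADA is listed among the primary safety and tolerability parameters (15.1.3). ADA and biomarkers are run centrally by a third-party laboratory (Table 2) on coded samples (12.13.6).
- *PD set.* Section 15.1.2 excludes patients with a deviation that has a major effect on PD results, which is a judgement. With 12 per group, one exclusion is 1/12 = 8.3% of an arm, in comparisons that 15.1.5 tests at the two-sided 10% level. Section 17.2 puts population definition before the freeze, but nothing expressly puts sign-off before the interim unblinding, and late biomarker results lie outside the interim lock.

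No alpha, power or sample-size figure changes.

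**The case against.** The strongest case against is that little is at risk. Dosing lasts at most 5 days and is finished, every Day 28 visit is complete, and adverse-event recording ends at Day 28 (13.4). The SAP is final before unblinding, the interim cannot stop the study, and the permission is worded as an option. The trial is an exploratory pilot without formal sizing. All of this stands, and it limits the point to an improvement in wording and access.

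A reader might infer more, in four ways that the documents do not support:

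- *That 15.4 flatly contradicts an absolute rule in 8.4.1.* The lock is undefined, so the sections are unreconciled, which is less than a proven contradiction. Nor is 8.4.1 absolute: it allows DSMB access and independent handling, and 10.6.2 allows emergency unblinding.
- *That analysis-set decisions are open at unblinding.* The order in 17.2, with the requirement in 15.4 for cleaned and locked data, suggests that they are closed for data inside the interim lock. What is missing is an express requirement, which matters for the late assays.
- *That assay results for all 48 patients will be read unblinded.* Section 15.4 says only that some may be late and does not name laboratories among those unblinded. No route to a biased reading is shown.
- *That the final data set is no longer double-blind.* Nearly all of it is collected before the codes open.

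The pending count is also soft. Patients who have died have no interview, which lowers it. Stage 1 is sequential with DSMB reviews, so stage 2 may recruit faster than average, which would raise it.

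**Conclusion.** The point holds in a limited form. Section 15.4 permits wider unblinding than its purpose needs while data are still to come, and 8.4.1, 10.6.1 and 15.4 do not agree on, or even state, which lock releases the blind. The exposed data are follow-up completeness, reported changes in condition for at most about 8-11 of 48 patients (about 4.5-6 with an assumed four weeks of cleaning), and PD-set exclusions that depend on late biomarker results.

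The counts rest on even accrual over 9-12 months and nominal visit days. No bias is quantified, and the documents give no basis for doing so. Section 15.4 leaves details of the interim to a separate SAP, whose text was not available for this check and which might settle part of this. This is a cheap improvement and does not show that the Day 28 results are unsound.

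**What to change.** - Amend 15.4 so that only a named sponsor and statistics group, not involved in data collection, sees allocation at the Day 28 analysis.
- Keep sites, patients, laboratories and the staff who classify deviations blinded until the lock that follows Day 90 and the pending assays. Retain the emergency provision in 10.6.2.
- Require deviation classification and PD/PK set membership to be signed off before the codes are opened, with a stated rule for patients whose assays are still outstanding.
- State in 8.4.1 and 10.6.1 which lock releases the blind, in the same terms as 15.4.

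The cost is protocol and SAP wording plus an access list that must be kept. Sites and patients learn allocation up to about two months later (62 days nominally). The Day 28 business decision is unaffected.

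Section 15.5 refers to an analysis already carried out, so the codes may have been opened, although the protocol does not say so. If they have, access cannot be restricted retrospectively. The remedy is then to document who knew allocation, from what date, and which Day 90 records, assay results and set decisions came later.

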15.5 Retrospective Collection of Data and Post-hoc Analysis

For exploratory analyses of nangibotide's efficacy for the treatment of septic shock, additional data will be collected on the following parameters:

- SOFA score: For all surviving patients, SOFA scores will be collected up to day 5. The purpose of this is to replace data that have been treated as missing in the original analysis.
- Duration of ICU stay: This is expected to provide efficacy data on a clinically relevant endpoint.

These data have not been collected in the original eCRF. They will be collected from source data at sites to the extent available.

The analysis of this data will follow the principles of the main analysis and will be further specified in a separate statistical analysis plan. The results will be reported separately.

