Cytokine distribution and vital signs over time are analysed by a repeated measures ANOVA (mixed models), if significant followed by the Bonferroni post-hoc test.

Data is tested for normality using Kolmogorov-Smirnov-test

HISTORY OF CHANGES

Changes from version 3.1 of the study protocol, dated 08 January 2018

- Introduction of retrospective data collection and exploratory post-hoc analysis of
 - Additional SOFA score data to replace data treated as missing in the original analysis
 - Duration of ICU stay
- Implementation of non-substantial change on plasma sample use documented on note to file dated 08 October 2018

Study protocol version 4.0 applies to study sites outside of France only

Changes from version 2.1 of the study protocol, dated 31 October 2017

- Addition of an interim analysis (section 15.4)
- Clarification of concomitant medication recording
- Minor corrections and clarifications

Study protocol version 3.0 dated 04 January 2017 applies to study sites outside of France only

Changes from version 1.3 of the study protocol, dated 12 September 2017

- Addition of blood samples for DNA analyses related to the TREM-1 signalling pathway
- Addition of a paragraph detailing the analysis and storage of blood samples
- Blood levels of sTLT-1 will not be analysed
- Name change of IMP management provider implemented
- Rating of Adverse Events updated for consistency with eCRF
- Minor corrections and clarifications

Study protocol version 2.0 dated 31 October 2017 applies to study sites outside of France only

Changes from version 1.2 of the study protocol, dated 29 August 2017

- Minor corrections and clarifications on the timing of blood samples in tables 1 and 2

These changes are **classified as non-substantial** by the sponsor according to the EU Clinical Trials Directive and section 8.2 of this study protocol.

Study protocol version 1.2, dated 29 August 2017 implemented the following changes from version 1.0 of the study protocol, dated 20 February 2017

- Changes requested by the French ANSM for sites in France:
 - Addition of exclusion criterion “APACHE II score <14”
 - Measurements of interferon- γ on days 1, 3, 5 and 28
 - Additional timepoint for the measurement of anti-drug antibodies on day 10
 - Direct antibody test (direct Coombs) at baseline (pre-dose), days 10 and 28
 - Addition of free bilirubin to the biochemistry laboratory parameters
 - Update of SUSAR reporting requirements for France
- Minor corrections and clarifications

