12.12 Duration of ICU Stay

The date and time of ICU discharge will be collected. This data will be collected to the extent available in source data and analysed post-hoc (see section 15.5).

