15.1 Statistical Methods

15.1.1 General Considerations

The analysis will be computed with SAS Version 9.4 (Copyright© 2013 by SAS Institute Inc., Cary, NC, USA).

Unless otherwise specified, baseline is defined as the last planned assessment prior to first dosing and no subgroup analysis is currently planned.

Missing safety, pharmacodynamic, pharmacokinetic and clinical data will not be replaced and will be treated as missing from summary and statistical analyses.

Unless otherwise specified, all treatment comparisons will be two-sided and significance will be assessed at the 5% level.

All safety, pharmacokinetic, pharmacodynamic and clinical data will be summarised by treatment group (Placebo, Dose level 1, Dose level 2 and Dose level 3), and visit, as appropriate.

Qualitative variables will be presented using the number of patients, the number of missing values, the frequency and the percentage per modality.

Quantitative variables will be reported using the number of patients, the number of missing values, the mean, the standard deviation, the median, the first and the third quartiles, the minimum and the maximum.

Between groups comparisons are calculated using an independent t-test or ANOVA-test for quantitative variables with a parametric distribution, or Mann-Whitney test or Kruskal Wallis-test for variables with a non-parametric distribution.

Data is tested for normality using Kolmogorov-Smirnov-test.

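### Duration of ICU stay is added as efficacy data with no rule for patients who die in ICU, so the comparison between arms is confounded by mortality

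*Combined protocol and SAP*

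**What the plan says.** Protocol version 4.0 lists the change in its History of Changes as "Introduction of retrospective data collection and exploratory post-hoc analysis of" additional SOFA data and duration of ICU stay. Section 15.5 gives the purpose of the second item: "Duration of ICU stay: This is expected to provide efficacy data on a clinically relevant endpoint".

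Section 12.12 names the new datum: "The date and time of ICU discharge will be collected". Section 15.5 adds that the retrospective items were not in the original eCRF: "They will be collected from source data at sites to the extent available".

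On analysis, 15.5 says: "The analysis of this data will follow the principles of the main analysis and will be further specified in a separate statistical analysis plan". The relevant principles are in 15.1.1. For missing data: "Missing safety, pharmacodynamic, pharmacokinetic and clinical data will not be replaced and will be treated as missing from summary and statistical analyses". For comparisons: "Between groups comparisons are calculated using an independent t-test or ANOVA-test for quantitative variables with a parametric distribution", with rank tests otherwise. The Clinical Analyses paragraph of 15.1.5 provides only descriptive statistics for the clinical parameters it lists.

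No section says how death in ICU is handled for this measure, and no time horizon is given. The SOFA item in 15.5 is restricted to survivors; the ICU item is silent. Elsewhere, ICU admission date is recorded at screening (11.2), date and time of death are recorded up to day 90 (12.10), and mortality at days 28 and 90 is a clinical parameter in its own right (15.1.3). Section 7 already names vasopressor-free and ventilator-free days.

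**The concern.** A stay in ICU ends in live discharge or in death. These are opposite outcomes, and a raw duration cannot tell them apart. With no stated rule, two handlings are open.

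- **No discharge date, so the value is missing.** Under 15.1.1 the patient drops out. The comparison is then among survivors, a group selected by an outcome that treatment may affect.
- **Death closes the stay.** The patient remains, but an early death scores as a short, apparently favourable stay.

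Neither gives a sound efficacy comparison. Sections 6.3 and 8.5.1 say the data will help design later studies, so a misleading dose signal on a measure labelled clinically relevant could carry forward.

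**Working it through.** **1. Sample size.** Each dose: 3 (stage 1) + 9 (stage 2) = 12. Placebo: 3 × 1 + 9 = 12. Total 4 × 12 = 48, which matches 9.1 and 15.2. The plan states no effect size or power for ICU stay, so there is no further figure to reproduce.

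**2. Assumed inputs.** None of these is in the documents.
- Survivors' stay is log-normal with median 8 days and log-SD 0.7, identical in both arms.
- Time to death is log-normal with log-SD 0.8. Its median d is varied.
- Mortality is 25% on placebo and 45% on a dose, with all deaths in ICU.

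The only mortality figure in the protocol is almost 30% (section 6.1). It is background for severe sepsis, not this trial's expected rate.

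**3. Deaths dropped.** Mean survivor stay = 8 × exp(0.7²/2) = 10.2 days in both arms. The equality follows from the assumption. The point is that 20 percentage points of extra mortality leave no trace.

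**4. Death as end of stay.** Mean stay = (1 − m) × 10.22 + m × d × exp(0.8²/2), where exp(0.32) = 1.377.

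| Median day of death | Mean time to death | Placebo (m = 0.25) | Dose (m = 0.45) | Dose appears |
|---|---|---|---|---|
| 4 | 5.5 | 9.0 | 8.1 | better by 0.9 |
| 6 | 8.3 | 9.7 | 9.3 | better by 0.4 |
| 8 | 11.0 | 10.4 | 10.6 | worse by 0.2 |
| 14 | 19.3 | 12.5 | 14.3 | worse by 1.8 |

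The sign changes where mean time to death equals mean survivor stay: d = 10.22 / 1.377 = 7.4 days.

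**5. Days alive and out of ICU to Day 28, death = 0.** For a survivor the expected value is 28·Φ(z) − 10.22·Φ(z − 0.7), with z = ln(28/8)/0.7 = 1.79, which gives 18.16 days. Placebo: 0.75 × 18.16 = 13.6. Dose: 0.55 × 18.16 = 10.0. The difference is 3.6 days in the right direction, whatever the value of d. This calculation counts every death as 0, including any after Day 28.

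**6. Noise at 12 per arm.** The variance of stay in each arm is that of the survivor/death mixture.
- Median death day 4: variances are about 60.5 and 54.1, so SE = √((60.5 + 54.1)/12) = 3.1 days. The 0.9-day shift is 0.3 SE, and the harmful dose shows the shorter mean in about Φ(0.3) = 62% of trials, against 50% by chance.
- Median death day 14: SE is about 5.4 days, so 1.8 days is also about 0.3 SE.
- Days alive and out of ICU: SE is about 4.1 days, so 3.6 days is about 0.9 SE.

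**7. A second set of inputs.** Mortality 30% vs 60%, log-SD 0.7 for both times, medians rather than means, by simulation.
- Deaths dropped: 8.0 vs 8.0 days, with 12 × 0.7 = 8.4 and 12 × 0.4 = 4.8 patients left. The dose has the shorter median in 49% of trials.
- Death as exit: 6.6 vs 5.3 days at median death day 4 (dose better in 72% of trials); 9.4 vs 11.2 at day 14 (dose better in 31%).
- ICU-free days: mean 12.7 vs 7.3. The harmful dose still has the better mean in about 9% of trials, or about 25% if its mortality is 45%.

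**The case against.** The strongest reply is that the documents adopt no faulty rule. They are silent on death in ICU, the two handlings are inferred, and a separate analysis plan is promised that may settle the matter. This stands in part: the plan has a gap, not a stated error. However, 15.5 already binds that later plan to the main-analysis principles, and those point to dropping such patients. The choice may also come late: 15.4 allows all parties to be unblinded after the last Day 28 visit, and 15.5 refers to an original analysis as already done.

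A reader might infer that harm will be presented as benefit. The documents do not support that. The favourable direction needs deaths earlier than survivors' discharge, and it reverses when deaths are late. Mortality has its own place in 15.1.3, deaths have a separate safety summary in 15.1.5, and no dose, stopping or success rule uses ICU stay.

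A reader might also infer that a significance test on ICU stay is certain. Section 15.1.1 gives general between-group tests, but 15.1.5 prescribes description for clinical parameters, so the comparison may be descriptive only. The confounding applies to a descriptive comparison as well.

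Finally, every numerical input is assumed, and at 12 per arm the shifts are small relative to noise. That is correct and limits the practical weight of the point. It does not make raw duration interpretable.

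**Conclusion.** The concern holds in this form: raw ICU duration is offered as exploratory efficacy data with no rule for death in ICU, the inherited default would drop patients with no discharge date, and the obvious alternative counts early deaths as short stays. Under either handling, mortality confounds the comparison between arms.

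In the illustration, 20 points of excess mortality appear as no difference among survivors. With death as exit, the dose looks anywhere from 0.9 day better to 1.8 days worse as the median day of death moves from 4 to 14. The sizes rest wholly on the assumed stay, death-time and mortality inputs. The dependence of the sign on when deaths occur is the firmer result.

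The item is exploratory, post-hoc and reported separately, and mortality is reported in its own right. The change should be made, but the primary safety conclusions do not depend on it.

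**What to change.** In 15.5, 12.12 and the post-hoc analysis plan:

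- Replace raw duration with days alive and out of ICU to Day 28, with death by Day 28 scored as 0. State the time origin.
- Support it with the cumulative incidence of live ICU discharge, with death as a competing event.
- Report mortality and the number of patients with missing ICU data by arm in the same table. Scoring death as 0 gives every patient who dies by Day 28 a value without a discharge date, so missing values are confined to survivors.
- If raw duration is still shown, show it descriptively only, beside mortality.

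The cost is wording. The ICU admission date (11.2), ICU discharge date (12.12) and date of death (12.10) are all covered by the protocol, and a free-days measure fits those already named in section 7. The summary is slightly less familiar than length of stay. Readmission days should not be required, because 12.12 collects only ICU discharge and subtracting later stays would need new data. The change makes the measure interpretable; it does not give 12 patients per arm the power to detect a difference.
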